8.6.2 Serious Adverse events (AEs)

The number of Serious Adverse Events (SA) and percentage of patients with at least one SAE be summarized by system organ class and by preferred terms (MedDRA).

8.6.3 Change in C-SSRS

The number of patients with C-SSRS ideation and behaviour scores compared to baseline will be summarized.

8.6.4 Laboratory parameters

Descriptive statistics of absolute value and change from baseline for laboratory values, including liver function parameters and INR, will be presented by follow-up time points.

The number and percentage of patients with changes in laboratory test results during the course of the study, i.e. change from normal to high or low, based on the local reference ranges will be summarized by assay concerned.

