### **5.3 Exclusion Criteria**

Patients meeting any of the following criteria will be excluded from the study:

1. Diagnosis of pericarditis that is secondary to specific prohibited etiologies, including tuberculosis (TB); neoplastic, purulent, or radiation etiologies; post-thoracic blunt trauma (e.g., motor vehicle accident); myocarditis
2. Estimated glomerular filtration rate (eGFR) <30 mL/min
3. Elevated alanine aminotransferase (ALT) or aspartate aminotransferase (AST) > 5 times the upper limit of normal (ULN) or ALT or AST >3x ULN plus bilirubin >2x ULN
4. Sepsis, defined as documented bacteremia at the time of screening or other documented active infection
5. Prior history of sustained ventricular arrhythmias
6. History of QT interval prolongation
7. QTc interval > 500 msec (please refer to Section 9.2.3 for bundle branch block, bifascicular block and paced rhythm correction)
8. Current participation in any research study involving investigational drugs or device
9. Inability or unwillingness to give informed consent
10. Ongoing drug or alcohol abuse
11. On any cannabinoid during the past month
12. Women who are pregnant or breastfeeding
13. Current diagnosis of cancer, with the exception of non-melanoma skin cancer
14. Any factor, which would make it unlikely that the patient can comply with the study procedures
15. Showing suicidal tendency as per the C-SSRS, administered at screening
16. On digoxin and/or type 1 or 3 antiarrhythmics
17. On immunosuppressive therapy with any of the following:
  - a. Rilonacept
  - b. Anakinra
  - c. Canakinumab
  - d. Methotrexate
  - e. Azathioprine
  - f. Cyclosporine
  - g. IVIG

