#### **9.2.11.3 *Drug-Induced Liver Injury (DILI)***

Wherever possible, timely confirmation of initial liver-related laboratory abnormalities should occur prior to the reporting of a potential DILI event. All occurrences of potential DILIs, meeting the defined criteria below, must be reported as SAEs.

Potential DILI is defined as:

1. ALT or AST elevation  $> 8 \times \text{ULN}$ 

OR
2. ALT or AST elevation  $> 5 \times \text{ULN}$  for more than 2 weeks

OR
3. ALT or AST elevation  $> 3 \times \text{ULN}$  and bilirubin  $> 2 \times \text{ULN}$  or INR  $> 1.5$ .

If a patient meets one of the above criteria, the study drug needs to be discontinued and the investigator is to arrange for the patient to return to the investigational site as soon as possible (within 24 hours of notice of abnormal results) for repeat assessment of ALT, AST, bilirubin and alkaline phosphatase, detailed history, and clinical assessment. Patients are to be followed in this way until all abnormalities have normalized (in the

investigator's opinion) or returned to the baseline state. If the patient cannot return to the investigational site, repeat assessments could be performed at a local laboratory (and the results are then to be sent to SOCAR by the investigator).

Elevations in ALT or AST  $> 3 \times$  ULN or bilirubin  $> 2 \times$  ULN alone, i.e., when not concomitant, are not grounds for withdrawal but are to be followed up, as above, within 72 hours of notice of abnormal results.

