8.6.5 ECG parameters

Descriptive statistics of absolute value and change from baseline of ECG intervals and rhythm during the 26-week study period.

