9 GENERAL PRINCIPLES

9.1 Standard descriptive statistics

The analyses will be presented/reported using summary tables, figures, and data listings. Continuous variables will be summarized with counts, means, standard deviations, medians, Interquartile range, minimums, and maximums.

Categorical variables will be summarized by counts and by percentage of patients.

All analyses and tabulations will be performed using SAS Version 9.3 or higher on a PC platform. Table, listings, and figures will be presented in RTF or Microsoft Word format. Upon completion, primary endpoints results will be validated by an independent programmer. In addition, all program output will undergo a senior level statistical review.

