Table 29 – Patients with a worsening of C-SSRS ideation and behaviour scores compared to baseline

Table 30 – Laboratory tests results (absolute and change from baseline) during the 26-week study period – Descriptive statistics

Table 31 – Patients who experience changes in laboratory parameters during the 26-week study period

Table 32 – ECG intervals (absolute and change from baseline) during the 26-week study period – Descriptive statistics

Table 33 – Vital signs (absolute and change from baseline) during the 26-week study period – Descriptive statistics

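### The laboratory shift count has no place for worsening from an abnormal baseline, and no planned table grades ALT, AST or bilirubin by multiples of the upper limit of normal

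*SAP*

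**What the plan says.** Protocol 4.2.2 names changes in laboratory parameters, including liver function and INR, among the safety parameters.

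SAP 8.6.4 plans two post-baseline laboratory outputs:

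- A continuous summary: "Descriptive statistics of absolute value and change from baseline for laboratory values, including liver function parameters and INR", by time point (Table 30, Figures 3 and 4). Under SAP 9.1, "Continuous variables will be summarized with counts, means, standard deviations, medians, Interquartile range, minimums, and maximums".
- A patient count, by assay. The title of Table 31 is broad, "Patients who experience changes in laboratory parameters during the 26-week study period", but 8.6.4 defines the change: "change from normal to high or low, based on the local reference ranges". Figure 5 charts the same count.

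The below/within/above-range table (Table 14) covers baseline only. SAP section 8 says that section 10 holds the complete set of outputs. Section 10 contains no table by ULN multiple and no listing of laboratory values (Listings 1 to 5).

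The protocol works in ULN multiples. Section 5.3 excludes ALT or AST above 5x ULN, or above 3x ULN together with bilirubin above 2x ULN. Section 9.2.11.3 makes three patterns potential drug-induced liver injury (DILI), to be reported as SAEs: ALT or AST above 8x ULN; above 5x ULN for more than 2 weeks; and above 3x ULN with bilirubin above 2x ULN or INR above 1.5. ALT or AST above 3x ULN alone, or bilirubin above 2x ULN alone, "are not grounds for withdrawal but are to be followed up", within 72 hours.

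**The concern.** The shift rule starts from normal. A patient whose ALT is already high at entry cannot meet it for that assay, however far the value climbs, yet the entry criteria knowingly admit such patients. The rule also has one step: just over the local limit and several times over it count the same.

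The protocol requires sites to follow up isolated ALT or AST above 3x ULN, but the SAP never counts how many patients got there. The safety objective is to show that the drug is safe at the proposed doses, and liver function is a named safety parameter. The report could therefore leave its reader unable to say how many patients crossed a threshold that the protocol itself treats as important.

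**Working it through.** The plan gives no laboratory event rate, alpha, power or sample-size calculation, so there is no figure to reproduce. The check applies the written rules to illustrative ALT paths.

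**Rules, with values in multiples of the local ULN**

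- Eligible (protocol 5.3): baseline at or below 5, bilirubin normal.
- Counted in Table 31 as a rise (SAP 8.6.4): baseline within range and post-baseline above 1.
- Potential DILI, hence SAE (protocol 9.2.11.3): above 8. The other two criteria are held off by assuming normal bilirubin and INR and no value above 5 for more than 2 weeks.

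| Baseline to peak | Eligible | In Table 31 | Above 3x | DILI SAE |
|---|---|---|---|---|
| 0.8 to 1.1 | yes | yes | no | no |
| 0.8 to 3.5 | yes | yes | yes | no |
| 0.8 to 7.9 | yes | yes | yes | no |
| 1.2 to 3.5 | yes | no | yes | no |
| 2 to 4.9 | yes | no | yes | no |
| 2 to 7.9 | yes | no | yes | no |
| 4.9 to 7.9 | yes | no | yes | no |
| 2 to 8.5 | yes | no | yes | yes |

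The first three rows share one Table 31 cell although their peaks run from 1.1x to 7.9x. The next four are eligible, pass 3x ULN, are absent from Table 31 and are not mandatory SAEs. The last is absent from Table 31 but reaches the SAE tables (27 and 28).

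Bilirubin has the same gap. Protocol 5.3 sets no bilirubin limit of its own, only one in combination with ALT or AST above 3x ULN, so a raised baseline bilirubin is admissible and its worsening has no cell.

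**Can the other outputs stand in?**

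- Table 30 shows the maximum value and the largest rise at each visit. SAP Table 8-1 reports ALT and AST in U/L, and several centers use their own local ranges. A maximum in U/L does not give a ULN multiple or a count of patients, and it cannot be tied to the same patient's bilirubin or INR.
- Tables 24 to 26 would hold a sub-DILI rise if it were reported as an AE. Protocol 9.2.11.1 allows an abnormal laboratory finding to be an AE but sets no liver-test level below DILI at which it must be.
- Tables 27 and 28 hold DILI-level rises whatever the baseline.

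**How likely is an isolated case above 3x ULN?** The documents give no rate. For an assumed true rate p in 25 patients, the chance of at least one is 1 − (1 − p)^25:

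- p = 2%: 1 − 0.98^25 = 39.7%
- p = 5%: 1 − 0.95^25 = 72.3%
- p = 10%: 1 − 0.90^25 = 92.8%

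These cover any baseline. Only cases from an abnormal baseline miss Table 31; the rest are in it, ungraded.

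**The case against.** The best case for the plan is that this is a small, open-label, descriptive pilot with several routes by which a liver signal can surface. Much of that stands.

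- A reader might infer that isolated ALT or AST above 3x ULN is in no planned table. The documents do not support that. From a normal baseline such a patient is in Table 31, and what is lost is the grade. DILI-level rises are mandatory SAEs. Lesser ones may be reported as AEs, and the follow-up duty puts them in front of the site.
- A reader might infer that visit means will hide single patients. Table 30 also gives minimums and maximums, so an extreme value will be visible, though without a count or a ULN multiple.
- A reader might infer that every patient with an abnormal baseline drops out. Table 31 is by assay, so a patient is outside the count only for the abnormal assay and stays in Table 30 throughout.
- One patient in 25 is 4%, and it is tempting to say that a reported rate falls from 4% to 0%. The SAP reports no rate above 3x ULN, so no such figure changes.
- The same complaint might be extended to QTc. Protocol 9.2.3 and 9.2.11.1 already make QTc crossings reportable SAEs (they differ only on whether exact equality counts), so the point does not carry over.

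What the objection does not answer is the middle ground: rises from an abnormal baseline that stay below the DILI criteria. Whether those are counted anywhere depends on the investigator's decision to report an AE.

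**Conclusion.** The concern holds as a gap in systematic counting, not as a loss of all liver information. No planned table has a category for worsening from an already abnormal baseline, and none grades ALT, AST or bilirubin by ULN multiple, although the protocol admits the first and acts on the second.

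The size cannot be stated as a rate, because the documents do not say how many patients have abnormal baseline values; the entry limit is a permission, not a forecast. No efficacy result, error rate or sample-size figure is affected.

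The conclusion assumes that the definition in 8.6.4 governs Table 31 despite its broader title, that section 10 is complete as section 8 states, and that the third DILI criterion means ALT or AST above 3x ULN with either bilirubin or INR raised. It is a worthwhile low-cost improvement.

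**What to change.** 1. Redefine Table 31, for each assay, as baseline category (low, normal, high) by worst post-baseline category, keeping baseline-abnormal patients in the table. Adapt Figure 5 to match.
2. Add one table of patients whose worst post-baseline ALT or AST is above 3x, 5x and 8x ULN; whose bilirubin is above 2x ULN; and who have ALT or AST above 3x ULN with bilirubin above 2x ULN or INR above 1.5. Use each site's own ULN.
3. Show baseline status in that table, preferably as a ULN band. The shift table alone is not enough: a rise from 2x to 4.9x is high to high there. Without the baseline band, a patient who enters at 4x and stays there would look like a new case.
4. State whether unscheduled repeat tests count towards the worst value, since the follow-up in 9.2.11.3 will generate some.

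The cost is one revised and one added table, with a matching change to Figure 5. SAP 8.3.10 already uses the results and local ranges needed, and no visit, test or clinical rule changes. The 8x and combined rows will partly repeat the DILI cases in Tables 27 and 28; that overlap also serves as a check on SAE reporting.

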8.6.5 ECG parameters

Descriptive statistics of absolute value and change from baseline of ECG intervals and rhythm during the 26-week study period.

8.6.6 Vital signs

Descriptive statistics of absolute value and change from baseline will be presented by follow-up time points.

9 GENERAL PRINCIPLES

9.1 Standard descriptive statistics

The analyses will be presented/reported using summary tables, figures, and data listings. Continuous variables will be summarized with counts, means, standard deviations, medians, Interquartile range, minimums, and maximums.

Categorical variables will be summarized by counts and by percentage of patients.

All analyses and tabulations will be performed using SAS Version 9.3 or higher on a PC platform. Table, listings, and figures will be presented in RTF or Microsoft Word format. Upon completion, primary endpoints results will be validated by an independent programmer. In addition, all program output will undergo a senior level statistical review.

9.2 Handling of missing data

Missing data will be treated as missing, not imputed, unless otherwise stated.

9.3 Precision

The precision of original measurements will be maintained in summaries. Where possible, means, medians and standard deviations will be presented with an increased level of precision; means and medians will be presented to one more decimal place than the raw data, and the standard deviations will be presented to two more decimal places than the raw data.

Percentages will be based on available data and denominators will exclude missing values. For frequency counts of categorical variables, categories where counts are zero will be displayed for the sake of completeness. For example, if none of the patients discontinue due to "lost to follow-up," this reason will be included in the table with a count 0. Categories with zero counts will not have zero percentages displayed.

9.4 Standard Calculations

Variables requiring calculation will be derived using the following formulas:

Study day – For a given date (date), study day is calculated as days since the date of first dose of study drug (firstdose):

- Study day = date – firstdose + 1, where date \geq firstdose
- Study day = date – firstdose, where date < firstdose

Days – Durations, expressed in days between one date (date1) and another later date (date2), are calculated using the following formula: duration in days = (date2-date1). This is because study intake starts during the afternoon and ends in the morning.

Weeks – Durations, expressed in weeks between one date (date1) and another later date (date2), are calculated using the following formula: duration in weeks = (date2-date1)/7.

Months – Durations, expressed in months between one date (date1) and another later date (date2), are calculated using the following formula: duration in months = (date2-date1)/30.4.

Minutes – Durations, expressed in minutes between one timepoint (time1) and another later timepoint (time2), are calculated using the following formula: duration in minutes = (time2-time1)/60.

9.5 Imputation of Dates

9.5.1 Adverse events

If year is present and month and day are missing (e.g XX-XXX-2020)

- If year = year of first dose, then set month and day to month and day of first dose unless end date is before date of first dose, in which case the onset date is set to 28 days prior to end date.
- If year < year of first dose, then set month and day to December 31st.
- If year > year of first dose, then set month and day to January 1st.

If month and year are present and day is missing (e.g XX-Jun-2022)

- If year = year of first dose and if month = month of first dose then set day to day of first dose date unless end date is before date of first dose, in which case the onset date is set to 28 days prior to end date.
- if month < month of first dose then set day to last day of month
- if month > month of first dose then set day to 1st day of month
- if year < year of first dose then set day to last day of month
- if year > year of first dose then set day to 1st day of month

9.5.2 Concomitant Medications

- If start date is completely missing: start date will not be imputed.
- If (year is present and month and day are missing) or (year and day are present and month is missing): set month and day to January 1.

Any partial dates will be displayed in data listings without imputation.

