7 STAGED STATISTICAL ANALYSIS (SSA)

As mentioned in section 1, the analyses for this trial will be done in a staged manner – i.e. the first analysis will be performed for data collected up to the week 8 visit and the second analysis will be done when the last patient last visit is performed and the database is declared ready for complete database lock. The following data will be presented in the SSA:

- Baseline data for all patients enrolled:
 - Patient demographics: age, gender, race, ethnicity
 - Past medical history: N (%) of patients by previous episodes of pericarditis category (i.e., 2, 3, 4, or >4);
 - N (%) of patients for whom medications at baseline were prescribed for pain and pericarditis: analgesics, opiates, NSAIDs, colchicine and corticosteroids. The medications concerned will be identified as those with following

Anatomical Therapeutic Chemical (ATC) classification: H02 (Corticosteroids for systemic use), M01 (anti-inflammatory and antirheumatic products), M04 (antigout preparations), N02A (Opioids), N02B (other analgesics and antipyretics)

- N (%) of patients prescribed medications for pain and pericarditis i.e. medications which were started up to and including the Week 8 visit date and for which the stop date was either empty or > enrolment date at the time of enrolment
- CRP value at baseline will be summarized as a continuous variable
- NRS scores at baseline will be summarized as a continuous variable
- Primary efficacy endpoint, i.e. the change in patient-reported pericarditis pain using an 11-point NRS from baseline to 8 weeks – see section 8.5.1.
- Additional efficacy endpoints (see section 8.5.2):
 - Patients with normalized CRP levels (i.e. with a CRP \leq 0.5 mg/dL) at 8 weeks (for patients with CRP \geq 1.0 mg/dL at baseline) will be summarized as a categorical variable.
 - Time to CRP normalization (in days – see section 8.5.2) up to the Week 8 visit date for patients with CRP \geq 1.0 mg/dL at baseline will be summarized as a continuous variable. If CRP had not normalized at the timepoint assessed in the analysis (e.g. week 8), the patients concerned was not included in the analysis - Time to CRP normalization
 - CRP change from baseline at 8 weeks will be summarized as a continuous variable.
- Study drug exposure:
 - N (%) of patients with highest tolerated dose of (up to Week 8 visit date):
 - 10mg/kg of body weight b.i.d.
 - 7.5mg/kg of body weight b.i.d.
 - 5.0mg/kg of body weight b.i.d.

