8.3.5 Concomitant medications

All medication data will be coded using the WHO Drug dictionary with the primary Anatomical Therapeutic Chemical (ATC) classification selected based on the route and indication.

All medication taken prior to the first dose of IMP intake, i.e with a stop date/time before the date/time of first IMP intake will be classified as prior medications.

For the purpose of classify medication, incomplete medication start and stop date will be imputed as detailed in Section 9.5.2.

Prior, baseline and concomitant medications will be summarized by providing the N and percentage of patients by therapeutic class (ATC second level, e.g. C03: Diuretics) sorted in alphabetical order of the therapeutic class.

All prior, baseline and medications prescribed as of the first IMP intake will be listed by study center, and patient number.

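### SAP 9.5.2 sets medication dates with the month missing to January 1, so a drug stopped after first dose in the same calendar year is classed as prior

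*SAP*

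**What the plan says.** SAP 8.3.5 states that "incomplete medication start and stop date will be imputed as detailed in Section 9.5.2", and gives classification as the purpose. In the same section, medications "i.e with a stop date/time before the date/time of first IMP intake will be classified as prior medications".

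SAP 9.5.2 holds the rules. The first bullet says "If start date is completely missing: start date will not be imputed". The second is triggered by "If (year is present and month and day are missing) or (year and day are present and month is missing"), and the action is to "set month and day to January 1". It does not say whether it means start or stop dates. Nothing in the section ties the imputed date to first dose, checks that a stop follows its start, or covers a date lacking only the day. Listings are to show partial dates as recorded.

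Two other places matter. The adverse event rule in SAP 9.5.1 is tied to first dose when the years match, and it is checked against the end date. The medication count in SAP 7 (staged Week 8 analysis) takes drugs "for which the stop date was either empty or > enrolment date".

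**The concern.** January 1 is the earliest possible day of a year. For a start date that is a common choice. For a stop date it shortens exposure as far as it can be shortened, and when the year is the year of first dose it moves the stop to the wrong side of first dose.

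This trial is exposed to that error by design. Patients must be on NSAIDs, colchicine or corticosteroids to enter (Protocol 5.2), those drugs are weaned in the extension period (Protocol 6.6), and rescue drugs may be added (Protocol 6.7). Stops and starts after first dose are therefore expected. The outputs at stake are:

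- the prior, baseline and concomitant medication summaries (SAP 8.3.5);
- Table 7;
- if they use imputed dates, the Week 8 count of pain and pericarditis medications (SAP 7) and the exploratory correlation of medications with NRS (SAP 8.5.3).

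With about 25 patients, one misclassified patient moves a percentage by 1/25 = 4 points.

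**Working it through.** The plan gives no figure to reproduce, so the check applies its rules to dates. The dates below are illustrative.

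**Rules applied.** Month missing: imputed date = January 1 of the recorded year (SAP 9.5.2, applied to starts and stops by 8.3.5). Prior: stop before first IMP intake (8.3.5).

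| Case | First dose | Truth | Recorded | Imputed | Result |
|---|---|---|---|---|---|
| A | 15 May 2023 | stopped 20 Aug 2023 | stop 2023 | 1 Jan 2023 | prior: wrong |
| B | 15 May 2023 | started 15 Mar 2023, stopped later that year | start complete, stop 2023 | stop 1 Jan 2023 | stop precedes start |
| C | 15 May 2023 | started 10 Jul 2023 | start 2023 | 1 Jan 2023 | appears to pre-date IMP: wrong |
| D | 1 Nov 2023 | stopped 20 Jan 2024 | stop 2024 | 1 Jan 2024 | not prior: right |
| E | 15 May 2023 | stopped in April 2023 | stop 2023 | 1 Jan 2023 | prior: right |
| F | 15 May 2023 | still taken | stop empty | none | not prior: right |

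The error needs three things together: the month is missing, the true date is after first dose, and the recorded year is the year of first dose (with first dose later than January 1).

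**How often, given a month-missing on-study date.** Assume first dose is equally likely on each of 365 days and the event equally likely on each of days 1 to H after it. Let k = 0, ..., 364 be the number of days from January 1 to first dose. The event stays in the same year on min(H, 364 − k) of the H days. First dose on January 1 (k = 0) gives no error.

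- H = 56 (8 weeks): 308 × 56 + (55 × 56)/2 = 17,248 + 1,540 = 18,788 of 365 × 56 = 20,440, or 91.9%.
- H = 182 (26 weeks): 182 × 182 + (181 × 182)/2 = 33,124 + 16,471 = 49,595 of 365 × 182 = 66,430, or 74.7%.

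Over 26 weeks the share depends strongly on when in the year the patient starts: 100% for first dose on 15 January, 1 April or 1 July; 91/182 = 50% for 1 October; 16/182 = 9% for 15 December.

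**After a change of rule.** Setting a month-missing stop to December 31, or a month-missing start to the first-dose date when the years match (as 9.5.1 does for adverse events), places 0% of these on-study dates before first dose at either horizon.

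**The case against.** Several points on the other side are sound.

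- **The stop-date reach comes from two sections.** Section 9.5.2 names only the start date, and its January 1 bullet names neither. One can read it as a start-date rule. But then 8.3.5 points to a stop-date rule that does not exist, and 9.5.2 still needs one.
- **The start-date effect is inferred.** SAP 8.3.5 does not define baseline medication. The general definition in 8.3 turns on when data were obtained, so a drug first reported at a later visit need not become a baseline drug. Nor can a start date make a drug prior, since that class depends on the stop alone.
- **The trigger may be rare.** Medication changes are recorded at every visit, scheduled visits are at most six weeks apart, and source data are verified (Protocol 9.1, 13.3.1). An unknown month is least likely for the pericarditis drugs that matter most.

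A reader might also infer more than the documents support:

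- *That ongoing drugs become prior drugs.* They do not. The January 1 rule needs a recorded year, so an empty stop date is never imputed, and SAP 7 counts it as current.
- *That every year-only stop in the year of first dose is misclassified.* Case E shows otherwise, and the one-month medication history taken at Visit 1 makes such records possible.
- *That on-study therapy is hidden.* Listing 4 covers these medications and listings show partial dates unimputed, so the raw record can be read for all of the roughly 25 patients.
- *That the efficacy result is at risk.* The primary NRS endpoint uses no medication dates, and no SAP endpoint measures weaning.

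**Conclusion.** The point holds in a narrow form. Read together, SAP 8.3.5 and 9.5.2 give a wrong class to a drug that was in use at first dose and stopped later in the same calendar year with the month unrecorded, and they can produce a stop before the start. A drug started on study and recorded by year only is made to look older than IMP. It would join the baseline drugs if the general definition in 8.3 is applied to the drug's start date.

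The size cannot be stated for the trial as a whole, because the documents do not say how many dates are partial. The 91.9% and 74.7% are conditional on an on-study date with the month already missing and on evenly spread dates; they are not error rates for all medication records. The lack of a rule for a missing day is a gap in detail, not a wrong result. This is a minor correction that affects descriptive medication tables and possibly one count and one exploratory analysis.

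**What to change.** Replace the single rule in SAP 9.5.2 with separate rules:

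1. **Stop dates:** set to the latest possible date, meaning December 31 if the month is missing or the last day of the month if only the day is missing, capped at last study contact.
2. **Start dates:** set to the earliest possible date. Exception: if the record was first reported after baseline and its partial date matches the year (or the month and year) of first dose, use the first-dose date, in line with 9.5.1.
3. **Consistency:** require the stop to be on or after the start.

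Rules 1 and 2 also cover the missing-day case. It would help to define baseline medication in 8.3.5, and to say in 7 and 8.5.3 whether imputed dates are used.

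The cost is a few lines of text and the matching programming. No new data are needed, assuming the visit at which each medication was first reported can be recovered from the eCRF. There is one small downside: a drug truly stopped before first dose in the same year with the month unrecorded (case E) would be counted as in use at first dose. Listing 4 would still show the date as recorded.
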